2.3 DETERMINATION OF SAMPLE SIZE

The main purpose of this study is hypothesis generation and estimation regarding the impact on pulmonary function in terms of the change in FVC, as measured by daily handheld spirometry, in patients suspected to suffer from IPF.

For this study, a total sample size of approximately 180 patients was planned (Table 2). The majority of the patients will be enrolled into two study cohorts, i.e., patients with a diagnosis of IPF or non-IPF ILD. Due to the uncertainty of the numbers of patients to be enrolled into these two cohorts, the sample size could not be derived for a certain patient number. For the purpose of sample size and power calculation, it was assumed that approximately 40% of patients will be diagnosed with IPF and 50% of patients will be diagnosed with non-IPF ILD. Approximately 10% of patients were expected to suffer from a disease other than ILD (non-ILD) or were expected not have a diagnosis within 12 months of enrollment. This assumption was based on published data (Wapenaar-deKorver et al. 2016).

Thus, it was expected to enroll approx. 72 patients with a diagnosis of IPF and approx. 90 patients with a diagnosis of non-IPF ILD. Approximately 18 patients may be diagnosed with non-ILD or have no diagnosis within the 12 months period following enrollment.

Table 2 Sample Size Scenarios

Number of patients with IPF	Mean FVC decline [mL] over 6 months	Lower Bound of 95% CI	Upper Bound of 95% CI	Total number of patients to be enrolled
72	25	8.83	41.17	180
72	50	33.83	66.17	180
72	75	58.83	91.17	180

CI = confidence interval

In Table 2 point estimates and 95% confidence intervals based on a normal distribution are tabulated for a range of possible outcomes, assuming 72 patients

analyzed, a standard deviation of 70 ml, and a precision of 16.17% (estimates produced using nQuery, version 7). A mean semi-annual FVC decline in the IPF group of 50 mL was considered to be a clinically relevant decline and a reasonable expectation in accordance with the literature (Ley et al. 2011). In addition, after inspection of historical data, it could be assumed that the common standard deviation in mean FVC decline was 70 mL as measured by handheld spirometry.

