4.2.3 Pre-diagnosis Assessment Period

From inclusion into the study (enrollment visit), patients will be followed for a maximum of 12 months in the pre-diagnosis assessment period. The length of the pre-diagnosis period will be derived as follows:

Pre-diagnosis period = date of diagnosis – date of enrollment visit + 1
or
= date of end of study visit – date of enrollment visit + 1

where diagnosis date is taken from the IPF/ILD diagnosis eCRF page.

In case the diagnosis date and/or end of study visit is missing and no diagnosis is documented for the patient, the pre-diagnosis period will be set to the maximum of 12 months.

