4.2.5 End of Study

For individual patients, the end of the study will be as follows:

- Should no diagnosis be made 12 months after inclusion into the study, the patient will leave the study and perform the end of study visit
- Patients diagnosed with a non-ILD condition will leave the study on the date of diagnosis

- Patients diagnosed with IPF or non-IPF ILD will remain in the study and be followed up to the start of drug treatment (within six months) or a maximum of six months if no drug treatment is prescribed

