4.4.3.4 IPF/ILD diagnosis

A listing and a frequency table will be provided for IPF and non-IPF ILD patients displaying details of the diagnosis (e.g. types of ILD, assessments used for diagnosis). In addition, information from working diagnosis for non-diagnosed patients will be tabulated and listed. Additionally, a Kaplan-Meier analysis is performed with respect to the time from enrollment to diagnosis, the time from enrollment to start of treatment, and time from diagnosis to start of treatment (for IPF and non-IPF ILD patients), presenting summary tables and corresponding KM plots separately by cohort. Thereby, the following rules for censoring will be applied:

- Time from enrollment to diagnosis (in weeks):

F. Hoffmann-La Roche Ltd
Statistical Analysis Plan MA39297, Final Version 2.0

Only diagnosed patients will be analyzed separately by cohort. For that reason, there will be no censoring observations.

- Time from enrollment to start of treatment (in weeks):

If a patient was diagnosed and did not start IPF/ILD treatment during the post-diagnosis period or is lost to follow-up, the patient will be censored at the time of the end of study visit, or at the last available visit during the post-diagnosis period. Frequencies of patients with events and without events, i.e. that treatment was initiated or not, will be presented together with the KM estimates.

- Time from diagnosis to start of treatment (in weeks):

If a patient was diagnosed and did not start IPF/ILD treatment during the post-diagnosis period or is lost to follow-up, the patient will be censored at the time of the end of study visit, or at the last available visit during the post-diagnosis period. Frequencies of patients with events and without events, i.e. that treatment was initiated or not, will be presented together with the KM estimates.

The duration of pre- and post-diagnosis periods is analyzed by use of a summary table.

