4.5.5 Subgroup Analyses

The different subgroups that will be used for subgroup analyses are described in detail within [Section 4.4.3.3](#)

The primary endpoint will be repeated for all agreed subgroups in [Section 4.4.3.3](#), as well as linear regression analysis using site spirometry data.

ILD/IPF diagnosis summary table, time from enrollment to diagnosis and time to treatment start (from enrollment and from diagnosis) will be reproduced by community/tertiary sites subgroup. Moreover, time from enrollment to diagnosis will be also presented by patients having/not having lung biopsy.

In addition, disease relevant optional assessments summary table will be created by community/tertiary sites subgroup and by country.

In an additional analysis it will be investigated if a FVC decline after three months can predict the annual decline in FVC for individual patients. In the publication from Russell et al. (2016) it is stated that “three-month rate of change predicts disease progression at 1 year”. This analysis will be performed for patients diagnosed with IPF or non-IPF ILD having a minimum of 1 year of observation time, i.e. patients with daily measurements collected for at least 1 year after baseline. The estimated 3 monthly decline and annual decline will be plotted and a Pearson’s correlation coefficient will be calculated. This analysis will be presented in the final analysis of the study.

For progressing and non-progressing patients, patients requiring respiratory-related hospitalizations and the different ILD subgroups, baseline characteristic tables (demographics, medical history, time to first IPF/ILD diagnosis and duration of pre- and post-diagnosis periods) will be repeated for the final analysis.

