From inclusion into the study, patients will be followed for a maximum of 12 months in the pre-diagnosis assessment period. Following thorough assessments and diagnoses, three groups of patients will be identified:

- Patients diagnosed with IPF.
- Patients diagnosed with an ILD other than IPF.
- Patients diagnosed with a condition that is not an ILD.

For individual patients, the end of the study will be as follows:

- Should no diagnosis be made 12 months after inclusion into the study, the patient will leave the study.
- Patients diagnosed with a non-ILD condition will leave the study on the date of diagnosis.
- Patients diagnosed with IPF or non-IPF ILD will remain and be followed in the study up to the start of drug treatment (within six months) or a maximum of six months if no drug treatment is prescribed.

“Start of drug treatment” is defined as the date when treatment commences. This includes the event of a patient receiving IPF or ILD drug treatment from a physician other than the investigator.

Accordingly, the total length of the study is variable for each patient, with a maximum of 18 months.

Site visits will be conducted at a minimum at baseline, diagnosis, and end-of-study for each individual patient. During each study period (pre- and post-diagnostic period), every patient should have at least one site visit, scheduled at the discretion of the Investigator. During these visits, any relevant information such as treatments given and results from HRCTs, radiographs, DLCO, lung biopsies etc. will be collected, as available.

The 6MWT and FVC measurements will be assessed on-site as per the Schedule of Activities (Appendix 1).

The study will be conducted under the leadership of a Steering Committee.

In the absence of the use of any therapeutic agent, an Independent Review Committee IRC/IRF or a Data Safety Monitoring Board (DSMB)/ Data Monitoring Committee (DMC) will not be needed in this study.

Patient study-specific assessments / study kit

Upon study enrollment, each patient will receive a study kit with a unique identifier containing the following:

- Hand-held spirometer (Device to measure daily FVC at home).
- Accelerometer (Device to continuously measure daily activities, such as steps per day, physical activity level).

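### On the enrollment clock, Kaplan-Meier time to treatment start censors untreated completers at about diagnosis + 6 months, so after month 6 the curve lies at or above the proportion who start treatment in the study

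*SAP*

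**What the plan says.** Section 4.4.3.4 plans Kaplan-Meier summary tables and plots by cohort for three times: enrollment to diagnosis, enrollment to treatment start, and diagnosis to treatment start. The two treatment outputs share one censoring rule. For patients who were diagnosed and either did not start treatment or were lost, "the patient will be censored at the time of the end of study visit, or at the last available visit during the post-diagnosis period". Counts of patients with and without treatment start are printed alongside.

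The censoring times follow from other sections:

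- Section 4.2.3: "patients will be followed for a maximum of 12 months in the pre-diagnosis assessment period".
- Section 4.2.5: patients with IPF or non-IPF ILD will "be followed up to the start of drug treatment (within six months) or a maximum of six months if no drug treatment is prescribed".
- Appendix 1: "the total length of the study is variable for each patient, with a maximum of 18 months".

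Section 4.5.5 repeats the outputs by type of site: "time from enrollment to diagnosis and time to treatment start (from enrollment and from diagnosis) will be reproduced by community/tertiary sites subgroup".

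**The concern.** Counted from diagnosis, the six-month cap falls at the same time for every completer and is ordinary administrative censoring. Counted from enrollment, it falls at about diagnosis + 6 months, anywhere from about month 6 to month 18.

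A patient diagnosed in month 1 and still untreated in month 7 leaves the risk set. Those who remain are mostly patients diagnosed later, some only just able to start treatment. Kaplan-Meier assigns their treatment rate to the patient who left, although that patient can no longer have a treatment start recorded in the study. The rule also pools patients who completed the window, whose in-study outcome is known, with patients who were lost, whose outcome is not.

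At stake is a descriptive curve, its late estimates and its median, overall and by community/tertiary site. A median time to treatment could be printed for a cohort in which fewer than half were treated.

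**Working it through.** **Inputs from the SAP.** Diagnosis falls in months 0-12 (4.2.3). Untreated follow-up after diagnosis lasts at most 6 months (4.2.5). The maximum is 18 months (Appendix 1). For the IPF cohort, "it was expected to enroll approx. 72 patients with a diagnosis of IPF", which reproduces as 0.40 × 180 = 72 (2.3). The SAP states no figure for time to treatment, so there is none to reproduce. The spread of diagnosis times and the share treated are assumptions below.

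**Step 1: direction, by hand.** Four patients are diagnosed at weeks 4, 4, 40 and 40. One of each pair starts treatment 8 weeks later; the other completes 26 weeks untreated. On the enrollment clock there are events at weeks 12 and 48 and censorings at weeks 30 and 66.

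- In-study proportion treated: 2/4 = 0.50.
- Kaplan-Meier from enrollment: S = (1 − 1/4) × (1 − 1/2) = 0.375, so 1-KM = 0.625.
- Kaplan-Meier from diagnosis: both events at week 8 with 4 at risk, so 1-KM = 2/4 = 0.50.
- Aalen-Johansen from enrollment, with completion untreated as a competing state: 1/4 at week 12. The probability of still being in neither state falls to 3/4 × 2/3 = 1/2 at week 30. At week 48, 1/2 × 1/2 = 1/4 is added. The total is 0.50.

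The two Kaplan-Meier curves give different final proportions for the same patients, with nobody lost. In general, Kaplan-Meier passes a censored patient's weight on to later times. So 1-KM(t) is never below (events by t)/n, and is strictly above it once a censoring precedes an event. No completer can be censored before month 6, so with no losses the two agree until then. If everyone were diagnosed at the same time, the excess would be zero.

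**Step 2: size, under stated assumptions.** Diagnosis time is truncated-exponential over 0-12 months (parameter 3 or 5 months) or uniform over 0-12 months. Between 40% and 70% are treated within 6 months of diagnosis, with an exponential lag (parameter 1.5 months, truncated at 6). There are no deaths or losses. The excess is 1-KM minus the proportion who have started treatment in the study by that time.

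| Months from enrollment | Excess, percentage points |
|---|---|
| up to 6 | 0 |
| 9 | about 1-4 |
| 12 | 5-11 |
| 18 | 12-19 |

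Example (60% treated, parameter 3 months): 1-KM is 0.70 at 12 months and 0.79 at 18, against 0.59 and 0.60. The differences are 0.70 − 0.59 = 0.11 and 0.79 − 0.60 = 0.19. About 4 of 72 patients are still at risk at 12 months and none at 18.

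**Step 3: the median.** With 40% treated, the large-sample Kaplan-Meier curve crosses one half at roughly 11-15 months, depending on the diagnosis-time distribution, although fewer than half are ever treated in the study. With 72 patients it will cross in some data sets and not in others. At 60-70% treated, the median moves by 0-1 month.

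**Step 4: a different target.** Suppose instead that the treatment rate is constant after diagnosis and continues unchanged beyond the window. In large samples 1-KM is then within 1-2 points of the extrapolated uptake, and slightly below it. With n = 72 and 50% treated by 6 months, it averages 0.71-0.78 at week 78 against an extrapolated 0.73-0.85. Against in-study uptake it is still 5-15 points too high at 12 months.

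**The case against.** The strongest reply is that the SAP never says 1-KM will be read as in-study uptake. The cap ends observation; it does not prevent later treatment, and censoring at the end of observation is the usual convention. This stands in part. A reader might infer that the late part of the curve is merely an artefact, but the documents do not support that: as step 4 shows, under a constant continuing rate the curve comes close to the extrapolated uptake. That reading, however, needs an assumption about a period nobody observes. The SAP neither states it nor names such a target, and the censoring still depends on the diagnosis date.

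Second, event counts are printed beside the curve, and 4.4.1 tabulates patients with and without treatment start. With no losses, the cumulative incidence curve would end at that same proportion. This reduces the harm, but the counts correct neither the path of the curve after month 6 nor its median.

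Third, the excess sits in a sparse tail, and its size rests on assumed rates. At n = 72 the sampling SD of 1-KM is 6-9 points at 12 months, so an excess of 5-11 points is comparable to sampling noise. This is correct and limits the priority.

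Fourth, a reader might infer that the site comparison is distorted only because of Kaplan-Meier and that another estimator would make the site curves agree. It would not. Any curve counted from enrollment includes the time to diagnosis, so sites that diagnose at different speeds differ under either method. Only the plateau would agree: with 60% treated in both groups, Kaplan-Meier ends at 0.78 (parameter 3 months) against 0.73 (uniform), whereas the cumulative incidence ends at 0.60 in both.

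**Conclusion.** The point holds in a limited form. The direction needs no assumed rates: relative to treatment start within the study, the enrollment-clock 1-KM is at or above the true proportion after month 6, and strictly above it whenever an untreated completer is censored before a later event. The sizes in step 2 rest on assumed diagnosis times, uptake and lag, with no losses. A slower, constant treatment rate over the window gives larger late gaps from in-study uptake (about 17-28 points at week 78, for 30-70% treated), but that is also the case in which the curve can be read as extrapolated uptake.

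The diagnosis-clock curve is unaffected. The curves are descriptive, sit under demographic and baseline characteristics, and are not among the endpoints in Table 3. The FVC primary endpoint is untouched. Low priority, but cheap to put right.

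**What to change.** In 4.4.3.4, for the enrollment clock:

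- State the target as treatment start within the study, that is, within 6 months of diagnosis, and label the curve so.
- Report the Aalen-Johansen cumulative incidence in place of 1-KM. Treat completing the window untreated and death before treatment as competing end states, and censor only patients lost earlier.
- Take any median from that curve, and report it as not reached where the curve stays below one half.

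Keep Kaplan-Meier for time from diagnosis to treatment. Make the same change to the community/tertiary repeat in 4.5.5.

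Cost: a few lines of SAP text and a standard procedure option, with no new data. Downside: the curve plateaus at the in-study proportion treated and says nothing about treatment after the window. If later uptake is of interest, it should be named as a separate target with its extrapolation assumption stated.

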4.4.4 Disease relevant optional assessments

Investigators can indicate whether disease relevant optional assessments have been performed for the patients, i.e. ECHO, Radiography, Bronchoalveolar lavage (BAL), BNP/NT-proBNP, high-resolution computed tomography (HRCT), lung biopsy or DLco assessment. A frequency table displaying the number of patients with optional assessments will be provided by diagnosis cohort. For results of optional assessments summary, frequency tables will be provided by diagnosis cohorts as appropriate.

4.4.5 Home measurements

A summary table over time will be presented to include the number of patients that chosen to see/continue to see his/her information on daily lung function and physical activity level.

4.4.6 Compliance

With respect to the home-based daily measurements compliance of patients will be investigated. It will be analyzed if gaps of measurements occur over time. A gap is thereby defined as 7 or more than 7 consecutive days of missing measurements and they are collected in the eCRF. A summary table displaying number of patients with gaps in daily measurements, number of gaps per patient (from 1 to the maximum number of gaps per patient) and duration of gaps will be provided by diagnosis cohorts for data from handheld spirometer and accelerometer. In addition, a bar plot will be

provided for spirometry and accelerometry data by cohort (IPF, non-IPF ILD, patients not diagnosed) specifying the daily data per patient and the number of gaps as collected in Cyberfish. All gaps will be included in the bar plot, even if they are of less than 7 consecutive days. The diagnosis date by patient will be also specified in the bar plot.

4.5 EFFICACY ANALYSIS

Generally, daily measurements by the patients are analyzed separately for the peri-diagnosis, pre-diagnosis and post-diagnosis periods (please refer to Section 4.2 for definition of periods). For the peri- and post-diagnosis period only IPF and non-IPF ILD patients are taken into account (since non-ILD patients and patients without diagnosis complete the trial at the end of the pre-diagnosis period). All measurements performed during site visits will be analyzed over the peri-diagnosis period only.

4.5.1 Primary Endpoints

The primary endpoint of the study is the time-adjusted semi-annual mean FVC decline (mL) in patients with IPF during the peri-diagnosis period (see Section 4.2) estimated from daily home spirometry measurements.

The semi-annual mean FVC decline is calculated by use of the estimated semi-annual FVC decline of each individual patient. The individual FVC decline is thereby estimated by applying a linear regression model to all acceptable FVC measurements flagged as 'Good blow' according to the MIR criteria (please refer to Section 2.2.1 for the definition of acceptable measurements) collected by the individual patient during the entire peri-diagnosis period, i.e.

$$X_{it} = \alpha_i + \beta_i D_{it} + u_{it}$$

where

X_{it} = the FVC measurements (mL) of patient i on day t , with $i=1, \dots, N$ and $t=1, \dots, T$

D_{it} = study day t of patient i

α_i, β_i = intercept and slope of the individual linear regression of patient i

The time-adjusted semi-annual decline for patient i is then obtained by estimating the patients' individual difference in predicted values between baseline (study day 0) and study day 183 from the linear regression:

$$\widehat{\Delta X}_{i,183} = \widehat{\beta}_i * 183$$

In a further step, the time-adjusted semi-annual mean FVC decline is estimated by calculating the mean over all individual time-adjusted semi-annual declines of all IPF patients.

A summary table displaying the semi-annual mean FVC decline during the peri-diagnosis period together with two-sided 95% confidence intervals based on percentiles of the t-distribution will be provided for IPF patients (primary analysis) and non-IPF ILD patients (secondary analysis). The same table is also provided for patients of all diagnosis cohorts for the pre-diagnosis period at 3, 6 and 12 months.

Further sensitivity analyses are specified under [Section 4.5.4](#).

A table displaying parameter estimates for the different diagnosis cohorts together with 95% confidence intervals and expected semi-annual and annual FVC values will be provided.

In order to investigate the individual development of home-based measured FVC values individual plots of the FVC values over time will be provided including the regression line and all quality blows with different colors, presenting a blue color for “Good Blows”, green color for “Don’t Start Too Early” manoeuvre, red color for “Avoid Coughing” manoeuvre. The diagnosis date will be presented in the plots with a vertical line.

4.5.2 Secondary Endpoints

The change in pulmonary function tests (FVC measured in mL by daily home spirometry) in patients with non-IPF ILD will be analyzed in the same way as the primary endpoint (see Section 4.5.1).

The change in FVC (mL and % predicted) measured by site spirometry will be analyzed in the same fashion as the primary endpoint for the peri-diagnosis period only (taking all visits into account). Therefore, these analyses will only be performed for IPF and non-IPF ILD patients. Additionally, a summary table of FVC values measured by site spirometry and changes from baseline will be provided by visit for all diagnosis cohorts (whereas for IPF and non-IPF ILD patients visits of the complete peri-diagnosis period will be displayed in contrast to non-ILD patients and patients without diagnosis where only visits of the pre-diagnosis period are available). In case more than one visit was performed during the pre-/post-diagnosis period, mean FVC values of these visits will be used for the derivation of descriptive statistics.

The correlation of FVC (mL) between home and site spirometry will be analyzed by taking into account the individually estimated linear regression models of each patient for home-based FVC measurements and site FVC measurements. The time-adjusted semi-annual declines for home and site FVC as described for the primary analysis will be

calculated for each patient. Pearson's correlation coefficient of these values will be estimated and displayed within a table. Please note that this analysis will be performed for the peri-diagnosis period only for IPF and non-IPF ILD patients.

The change in 6MWT will be analyzed descriptively over time. A summary table displaying descriptive statistics for SpO₂ at rest (%), distance walked (m), SpO₂ at the end of the test (%), oxygen requirements (L), and Borg scale and changes from baseline over visits will be displayed by diagnosis cohorts. In case more than one visit was performed during the pre-/post-diagnosis period, mean parameter values of these visits will be used for the derivation of descriptive statistics.

In order to investigate the timely development of physical functional capacity measurements, individual graphs of the number of steps/day by patient will be also provided.

Additionally, the correlation between physical functional capacity assessed at home, i.e. the number of steps per day and on site (distance walked based on the 6MWT), will be analyzed by calculating Pearson's correlation coefficient, analogously to the correlation analysis of home and site spirometry measurements. Please note that this analysis will be performed for the peri-diagnosis period only for IPF and non-IPF ILD patients.

For the K-BILD questionnaire a frequency table of the individual items is provided by visit and diagnosis cohort. Additionally, a summary table of K-BILD total scores and subscores and changes from baseline and from diagnosis is given by visit and diagnosis cohort.

Outcomes and changes over time of the mMRC Dyspnea Scale and for the patient status are analyzed by use of shift tables from baseline and from diagnosis visit over time. Separate tables will be provided for each diagnosis cohort.

GAP score will be presented over time by visit together with the corresponding change from baseline and from diagnosis visit.

For the EQ-5D-5L questionnaire a frequency table displaying outcomes of individual items of the questionnaire will be given by visit and diagnosis cohort. For the index utility score values derived from the individual health state profiles of the EQ-5D-5L and the VAS values, separate summary tables will be provided by visit including changes from baseline and from diagnosis visit over time. In addition, line graphs per cohort will be presented for the EQ-5D-5L index utility score and VAS score.

Summary tables by visit and changes from baseline and from diagnosis visit over time will also be displayed by diagnosis cohort for outcomes of the Fatigue Assessment Scale (FAS), the cough, urge to cough and the Fatigue Visual Analogue Scales (VAS).

